Our overarching approach to combine insights from clinical and patient groups with advanced analytical methods used successfully in the NIHR-funded ESORT study evaluating emergency surgery ([name], [name], [name] & [name], 52-54). The ESORT study showed the importance of input from clinicians and patients in defining the main elements of the target trial's protocol, including eligibility criteria, and the treatment strategy protocols. For the assessment of the effectiveness of curative RT versus surgery, we will adjust for differences between the comparison groups in measured patient and organisational factors. However, we recognise that there is a risk of residual confounding from unmeasured differences between the comparison groups. We will address this risk of residual confounding in an instrumental variable analysis. An instrumental variable encourages receipt of the intervention, but does not have a direct effect on the outcome. The ESORT study showed how an instrumental variable analysis could reduce the risk of confounding when comparing outcomes from routine data (53,54). The proposed research draws on work by co-applicant [name] (41), who found that as curative RT requires more outpatient visits than surgery, patients who have to travel further may be less likely to receive curative RT. We will use the patient's travel time to the nearest RT centre, as an instrumental variable to minimise residual confounding after adjusting for all measured organisational and patient factors (see also WP 3).

4. Aims and objectives

The aims are to evaluate the impact of the COVID-19 period on inequalities in the use of curative interventions, and to assess the relative effectiveness and cost-effectiveness of RT versus surgery for patients with early-stage NSCLC, OSCC and MIBC.

For patients with these early-stage cancers, the objectives are:

- 1. To describe the influence of patient and organisational factors on the use of curative RT, curative surgery or non-curative strategies
- 2. To assess inequalities in the receipt of curative versus non-curative interventions
- 3. To assess the effectiveness of curative RT versus curative surgical strategies
- 4. To assess the cost-effectiveness of curative RT versus curative surgical strategies

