Secondary outcomes will include: all-cause and cancer-specific mortality at 30 days, 90 days, 12 months, and 24 months, time to death, and the number of days in hospital prior to 12 months, as this may be associated with grade three or four adverse events. We will use life tables in England according to calendar year, region, age, gender, deprivation and ethnicity to calculate rates of net cancer survival, which recognise the excess risks of death following a cancer diagnosis, versus those for the general population [66].

Effect size	Standard	_	Levels c	of compliance (IV	strength):
(three-year mortality difference in level of absolute risk)	deviation of the outcome in the population	Proportion of patients receiving RT	0.5	0.6	0.7
5%	0.3	0.5	4,521	3,140	2,307
5%	0.4	0.5	8,037	5,581	4,101
5%	0.4	0.6	8,372	5,814	4,271
10%	0.3	0.5	1,130	785	577
10%	0.4	0.5	2,009	1,395	1,025
10%	0.4	0.6	2,093	1,453	1,068

Table 3: Required sample size (N) for the IV design according to instrument strength(level of compliance) and magnitude of effect size at 80% power

WP 3.2 Quantitative analysis of the target trials (leads [name], [name], advisor [name] developer of the local instrumental variable method)

The analysis will recognise that even after applying the target trial inclusion criteria, and adjusting for measured covariates, the choice of curative RT versus surgical treatment will reflect some organisational (e.g. MDT composition) or patient factors (e.g. patient preference) that are not available within the linked data. We will use the instrumental variable approach taken in the ESORT study to address this form of confounding by indication due to unmeasured factors that commonly arises with routine data (52-54,64).

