The instrumental variable approach will be set out in a Statistical Analysis Plan. In brief, we will draw from previous research that has used distance or travel time, as an instrumental variable for treatment choice (67). Recent work by co-applicant [name] found that travel time to the nearest RT centre from a patient's area of residence predicted whether they had curative RT or surgery (41). Our PPI colleagues have emphasised that increased travel time may discourage patients from having curative RT versus surgery as this requires more outpatient visits. We will calculate a continuous measure of travel time from the patient's area of residence to the nearest NHS trust that provides curative RT (see WP1). We will use this measure of travel time as an instrumental variable for the receipt of curative RT versus surgery. This instrumental variable will be combined with adjustment for measured covariates to minimise bias from unobserved confounding in comparing 3-year mortality following curative RT versus surgery, for eligible patients with each of these three early-stage cancers.

Box 1: Results from Pilot work supporting the Instrumental Variable approach

We undertook *preparatory work* using the 2014-17 national linked cancer data for early stage OSCC which has the smallest sample size across the 3 conditions, and hence presents a greater challenge for the instrumental variable approach. We found that the essential assumptions for travel time to be an instrumental variable were realistic. *First*, the travel time from the patients' area of residence to the nearest NHS trust providing curative RT was associated with receipt of curative RT versus surgery (F statistics >20 versus the recommended cut-off of >10). *Second*, travel time balanced prognostic measures such as the patients' cancer stage. We will repeat these assessments on the final linked data for all three conditions, which given the larger sample sizes would be anticipated to yield a stronger instrument. The assumption that travel time is independent of unmeasured confounders cannot be assessed empirically, but is likely to be justified, since after accounting for measured baseline variables (geographical place of residence, deprivation level, time period, 'centre' and other quality of care variables), it is unlikely that travel time direct predicts all-cause mortality. This assumption will also be discussed with the clinical panels (W1) (see also sensitivity analyses).

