WP 3.3 Estimating effectiveness of curative RT versus surgery for each tumour type

The three target trials will report differences between the comparison groups according to absolute risk differences for three-year mortality (primary endpoint) and other binary measures, and difference in means for continuous measures (secondary endpoints). We will use a local instrumental variable approach to estimate the relative effectiveness of RT versus surgery for each individual, as this approach can fully account for confounding and heterogeneity across patient subgroups (54). We will report relative effectiveness across all patients included in each target trial, and for each pre-specified subgroup of interest: tumour size and spread to nearby lymph nodes and/or to distant sites, age (years), performance status, smoking status, Charlson comorbidity index, and year of diagnosis. This analysis will

be conducted according to the intention-to-treat principle, recognising that patients may experience delays in the receipt of either curative intervention, may not complete their allocated treatment or may switch from one treatment option to the other. Following this principle, we will include all patients from the time they meet the inclusion criteria, and adjust for covariates anticipated to predict the assigned treatment and the outcome, according to their observed level at baseline (time zero).

The local instrumental variable approach comprises two stages. In the first stage, Probit regression models will be used to estimate the initial propensity score as a function of covariates and the IV. In the second stage, this predicted propensity score will be included alongside covariates in Generalised Linear Models with appropriate link functions for continuous or binary outcomes. Models at both stages will adjust for case-mix, organisational-and temporal factors described above including time period, proxies for care quality, defined by rates of 30-day and 1-year mortality for each NHS hospital trust for the early-stage cancers in question, for the year prior to the individual's diagnosis. The estimates will be reported with bootstrapped confidence intervals that allow for the clustering of individuals within NHS trusts and cancer alliances, and with multiple imputation to allow for missing covariate information.

WP 3.4 Sensitivity analyses

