Sensitivity analyses will be undertaken to assess whether the results are robust to alternative definitions and assumptions. First, alternative inclusion criteria with respect to the time to curative treatment will be applied, including stricter (within three months of diagnosis), and looser (within nine month) cut-offs. Second, we will consider as an alternative instrumental variable, the percentage of eligible patients receiving RT versus surgery in each NHS trust in the year preceding the individual patient's diagnosis. Third, rather than using an instrumental variable analysis, the study will instead undertake conventional risk adjustment assuming that all relevant confounders have been measured, while assessing the impact of plausible levels of unobserved confounding on the results. Fourth, as in WP2, we will exclude data from the first wave of COVID-19 in England to assess the extent to which the results are sensitive to the inclusion of this period that is anticipated to be atypical for the provision of cancer services.

WP 3.5 Output and Interpretation of results (leads [name], [name], [name], [name], [name], [name])

We will report the relative effectiveness of RT versus surgery according to differences in absolute risk of 3-year mortality for each cancer. In interpreting the results, we will draw on insights from the clinical panels, and patient interviews, about the influence of local organisational factors and patient preferences on curative treatment decisions. The interpretation of the results will be according to the specific time-period. This will be important to provide recommendations for periods when the NHS is under exceptional pressures, such as during the first wave of COVID-19, and under prolonged pressures; for example, the increasing waiting lists for cancer care during the subsequent waves of COVID-19.

WP 4: Cost-effectiveness (Objective 4) (lead [name] and [name] advisor on combining inequality and costeffectiveness)

The cost-effectiveness analyses (CEA) will take the NHS and Personal Social Services perspective recommended by NICE. For each early-stage cancer we will report the relative cost-effectiveness of curative RT versus surgery strategies, over a lifetime time horizon. The choice of comparators will not include a 'no curative treatment alternative' as this is not a recommended treatment alternative for people with these early-stage cancers. The study will

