incorporate patient-level resource use and mortality data from the linked dataset, combined with unit costs and health-related quality of life (HRQoL) estimates from the literature (68-73). The CEA will follow the assessment of effectiveness, in using travel time as an instrumental variable to address confounding. The value of implementation analysis will incorporate the findings about inequalities (WP1), to report the value of increasing the uptake of the most cost-effective curative intervention for each cancer, within sociodemographic groups (e.g. according to deprivation-level).

WP 4.1 Resource use and unit costs

The linked datasets will identify resource use data for those categories anticipated to drive incremental costs, including the delivery of radiotherapy, surgical treatments, systemic care, hospital inpatient stays, and outpatient visits. Data for all types of external beam radiotherapy, doses, and fractions delivered to eligible patients will be extracted. We will identify the OPCS code of all surgeries and operative procedures performed on each eligible patient. We will obtain the drug administered, dose, number of cycles, and route of administration for patients undergoing chemotherapy including pre- or perioperative therapies, as well as those with curative and palliative intent. Information from the linked dataset on all hospitalisations since the date of cancer diagnosis will be extracted. We will distinguish between the time spent in critical care and on general wards, and all outpatient visits and accompanying medical procedures (e.g. imaging),

Unit costs, including those for RT and surgical strategies, will be taken from the NHS National Costs Collection (74) and the PSSRU Unit Cost databases (75). We will combine resource use with unit costs to report total costs per patient for the maximum duration of follow-up.

Outcomes

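### Travel time is defended as an instrument for mortality only, yet it is also used for hospital days, NHS costs and net benefit

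*Protocol*

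**What the plan says.** Protocol section 3.4 gives the condition that the instrument must meet: "An instrumental variable encourages receipt of the intervention, but does not have a direct effect on the outcome". Box 1 (WP 3.2) argues that the condition holds. It lists the baseline variables to be accounted for (place of residence, deprivation, time period, centre and other quality-of-care variables) and concludes that "it is unlikely that travel time direct predicts all-cause mortality". No other outcome is named there.

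The instrument's strength is explained by visit burden: "increased travel time may discourage patients from having curative RT versus surgery as this requires more outpatient visits" (WP 3.2).

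The same instrument is then used more widely:

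- WP 3.1 lists as a secondary outcome "the number of days in hospital prior to 12 months, as this may be associated with grade three or four adverse events", and WP 3.3 puts continuous secondary endpoints through the same local instrumental variable method as mortality.
- WP 4 carries it into the economic evaluation: "The CEA will follow the assessment of effectiveness, in using travel time as an instrumental variable to address confounding". On perspective it says: "The cost-effectiveness analyses (CEA) will take the NHS and Personal Social Services perspective recommended by NICE". The resource categories in WP 4.1 include "delivery of radiotherapy, surgical treatments, systemic care, hospital inpatient stays, and outpatient visits".
- WP 4.2 extends the instrumental variable analysis to the INB.

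WP 3.4 plans two analyses that do not rely on travel time: one uses each trust's radiotherapy share in the preceding year as the instrument, the other uses conventional risk adjustment. The sensitivity analyses of WP 4 repeat the WP 3 scenarios. They also add a societal perspective that brings in patient costs, with travel time given as an example.

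**The concern.** The no-direct-effect (exclusion) condition belongs to a pair, one instrument and one outcome. An argument that travel time does not itself change the risk of death says nothing about whether it changes how many clinic visits a patient attends or when a patient is discharged. For resource use a direct path is easy to imagine: the burden that shifts the choice of modality could also affect follow-up attendance or length of stay among patients who have had the same treatment.

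The stake is the INB. Its survival component can lean on the Box 1 argument, but its cost component cannot. An instrumental variable estimate attributes any direct effect on cost to the treatment. The value of implementation analysis then takes whichever option is more cost-effective and values raising its uptake to 100%, so an error in the sign of the INB would carry through to the recommendation.

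**Working it through.** **Inputs.** Compliance of 0.5, 0.6 and 0.7 and power of 80% come from Table 3. Alpha is not stated, so two-sided 0.05 is assumed. The documents give no figure for a direct effect of travel time on hospital days or cost. Every such value below is an assumption.

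**1. The plan's own figure.** Table 3 follows from

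N = (1.960 + 0.842)² × SD² / [p(1 − p) × δ² × c²],

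with p the radiotherapy share, δ the risk difference and c the compliance. For δ = 0.05, SD = 0.3, p = 0.5 and c = 0.5:

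N = 7.849 × 0.09 / (0.25 × 0.0025 × 0.25) = 4,521, as printed.

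All 18 cells reproduce to within one patient. The table concerns mortality and is not in dispute. It does show that the plan's working model is the simple one in which the contrast across the instrument equals c times the treatment effect. The same model is used below.

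**2. Which outcomes the argument covers.**

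| Outcome | Travel time is the instrument | No direct effect argued |
|---|---|---|
| All-cause mortality | Yes (WP 3.2, 3.3) | Yes (Box 1) |
| Days in hospital to 12 months | Yes (WP 3.1, 3.3) | No |
| NHS costs, base case | Yes (WP 4, 4.1) | No |
| INB | Yes (WP 4.2) | Survival part only |

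The named care-quality proxies in WP 3.3 are also mortality rates (30-day and 1-year, by trust). None describes length of stay or outpatient intensity.

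**3. Size of the bias.** Let β be the true treatment effect and γ the direct effect of the instrument on the outcome (near minus far, after adjustment). The contrast across the instrument is cβ + γ. Dividing by c gives β + γ/c, so the bias is γ/c. The multiplier 1/c is 1/0.7 = 1.43 to 1/0.5 = 2.00.

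| Assumed γ | c = 0.5 | c = 0.6 | c = 0.7 |
|---|---|---|---|
| 0.25 day | 0.50 | 0.42 | 0.36 |
| 0.5 day | 1.00 | 0.83 | 0.71 |
| GBP 100 | 200 | 167 | 143 |
| GBP 500 | 1,000 | 833 | 714 |

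**4. Check by simulation.** With 2,000,000 patients, a true effect of 2 days and no direct effect, the Wald estimate was 1.99 at c = 0.5 and 2.00 at c = 0.7. With a direct effect of 0.5 day it was 2.99 and 2.72, against predictions of 2 + 0.5/0.5 = 3.00 and 2 + 0.5/0.7 = 2.71. At that sample size random error is negligible, so the excess is bias and more data would not remove it.

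**5. Sign.** Distant patients receive less radiotherapy. If they also attend fewer visits within each arm, radiotherapy looks more costly than it is. If they stay longer in hospital, it looks less costly. The two paths oppose each other and the documents do not say which is larger.

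**6. Break-even.** If γ is the direct effect on net benefit, the corrected INB is INB − γ/c, which reaches zero at γ = c × INB. For an assumed estimate of GBP 1,000 and c = 0.5, that is GBP 500. This is the quantity that a reader of the INB needs, and it can be computed from the planned outputs.

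**7. Societal analysis.** Patient travel cost is roughly visits × travel time × value of time. With treatment and number of visits held fixed, it still changes with travel time. For this component the instrument is part of the outcome, so exclusion fails by construction and not merely by conjecture.

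**The case against.** The strongest reply has five parts.

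- **The instrumental variable method is deferred to an SAP.** WP 3.2 describes it only in outline, and outcome-by-outcome exclusion arguments are normal SAP content. This stands as far as detail goes. But the protocol itself fixes travel time as the instrument for costs and sets out a validity argument that does not reach them.
- **The plan never says that travel time acts directly on resource use.** This stands. A reader might infer from the visit-burden passage that the plan concedes a direct effect on attendance. The text speaks only of the choice between modalities, which is the path an instrument is meant to work through. An effect within an arm is a plausible inference and no more.
- **The residual direct effect may be small.** The instrument is travel time to the nearest radiotherapy provider. Follow-up and admissions may happen elsewhere in a hub-and-spoke service, and Box 1 accounts for residence, deprivation and centre. This is fair, and it is a reason to give a range and not a single correction.
- **Cross-checks already exist.** The trust-share instrument and risk adjustment are repeated for the economic evaluation, and Box 1 sends the independence assumption to the clinical panels. Disagreement between the two instruments on cost would be a warning. It could not, however, separate a direct travel effect from confounding or from a fault in the other instrument. The bias assessment in WP 3.4 concerns unobserved confounding under risk adjustment, not exclusion.
- **The Wald ratio is a simplification.** The plan uses a continuous instrument, a probit first stage and a generalised linear second stage. The method still needs exclusion, but the multiplier need not be exactly 1/c.

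**Conclusion.** The point holds in a limited form. Exclusion is argued for all-cause mortality only, while the same instrument is used for hospital days, base-case NHS costs and the INB without an argument for them. A direct path is plausible for these outcomes but is neither stated nor quantified. If one exists, its effect is magnified about 1.4 to 2 times at the plan's compliance, under a simple Wald model, and persists in any sample. The planned cross-checks do not size it. In the societal sensitivity analysis the violation is certain for patient travel costs if travel time remains the instrument.

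Two stronger conclusions are tempting and unsupported. One is that the analysis is biased in a known direction, for example against radiotherapy; the opposing paths leave the sign open. The other is that the bias is very large, as it would be at a compliance of, say, 0.1. Table 3 uses 0.5 to 0.7, and WP 3.1 expects higher compliance in the full data than in the pilot. The day and GBP figures above illustrate scale and are not estimates.

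**What to change.** 1. Add to the sensitivity analyses of WP 3 and WP 4 a 'plausibly exogenous' analysis, meaning one that lets the instrument have a direct effect of stated size. Report hospital days, incremental cost and INB over a range of direct travel-time effects fixed in advance, including the value at which the INB changes sign.
2. Present the cost and INB results from the trust-radiotherapy-share instrument and from risk adjustment beside the travel-time result.
3. In the societal analysis, do not estimate patient travel costs with travel time as the instrument.
4. Do not correct the INB with a direct effect estimated in the WP 2 non-curative group. WP 2.1 places there every intervention that fails the curative criteria, which takes in radiotherapy below the curative dose and treatment later than six months. Membership may also depend on travel time, since WP 2.2 adjusts for distance when modelling receipt of curative treatment. Use that group at most as an exploratory check.

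Items 1 and 2 use data and analyses already planned. The cost is a wider reported range for the INB.

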6.1 Dissemination

We will use findings from all four WPs to develop recommendations for each cancer about:

- the major organisational barriers that need to be addressed to improve access to either curative intervention

- the curative treatment strategy that is more effective, and more cost-effective

-the sociodemographic groups that have low uptake of the curative intervention that is more cost-effective

--improving patient experiences of the curative treatment pathway, for example in the provision of accessible information to underserved groups.

We will publish seven open access peer-review journal articles (patient interviews, descriptive analysis of the receipt of curative and non-curative treatments, inequalities, impact of COVID on inequalities, effectiveness, cost-effectiveness, overall recommendations for policy and patients). The target journals will include clinical, social science, policy and health economics journals. We will work with our PPIE co-applicants, the Centre for Ethnic Health Research, the National Cancer Research Institute (NCRI) Consumer forum, and with representatives from national charities to co-produce accessible, culturally sensitive and appropriate easy read documents, videos, infographics and lay summaries. We will co-produce recommendations for implementation of our findings with professional bodies and

PPIE co-applicants which will be made available on our own project website (e.g. sort.lshtm.ac.uk), and those hosted by national cancer charities, and the NCRI.

